## 1. Introduction

---

Fear of the syringes and needle insertion is high among children. Reducing injection pain in children may help to provide overall comfort and well-being during the entire dental experience. Pediatric dentists are constantly searching for tools that may provide a more comfortable dental procedure. A local anesthetic injection is one of the potent techniques to alleviate pain, but injection of local anesthetic itself is a major source of patient's fear.

The challenge is to find an effective method that can be utilized in the pediatric population. Topical anesthetics function by blocking signal transmission in the terminal fibers of sensory nerves. Their effects are limited to the control of painful stimuli occurring in or just beneath the mucosa.

Over the years, topical anesthetics have been used consistently in dentistry to prepare injection sites before needle penetration. Some studies have proved topical anesthetic capability in reducing pain perception during injections; however, others have concluded that topical anesthetics afford little more than placebo levels of effectiveness. can be employed as a supplementary anesthetic technique to reduce intraoperative pain.

Cryotherapy application is another endorsed strategy for reducing pain perception in patients that would be effective, efficient, and cost-effective.

Cryoanesthesia is the application of ice on the anesthetic site to counter nerve conduction of pain from the site. Studies have reported that it lowers edema, nerve conduction velocities, cellular metabolism, and local blood flow. The application of ice provides physiological and psychological benefits to the patients as it may distract them from focusing on their discomfort. Their use is much less widespread in dentistry; nevertheless, the use of ice sticks, refrigerants, or vapocoolants in the dental operatory to provide pre-injection anesthesia has been described in the literature.

The methods used currently for topical anesthesia before dental injections mainly include different types of gel (e.g., lidocaine, prilocaine, or benzocaine 20% (BC)). Unfortunately, these gels tend to spread in the mouth due to lack of bio-adhesion, which may result in a reduced anesthetic effect, unpleasant taste, and/or discomfort for the patient. Furthermore, there is a risk of allergic reactions to several components in the different gels available for topical anesthesia. These factors are important reasons for developing and evaluating other substances and techniques for topical anesthesia. Ice was introduced during the nineteenth century as a safe method of local anesthesia, and the use of cooling to reduce injection pain in the skin is well documented.

Several explanations for the anesthetic effect of cooling have been proposed. The topical cold application stimulates myelinated “A” fibers, thereby activating inhibitory pain pathways, perhaps as part of the gate control system at the spinal cord level. Furthermore, cooling causes cold-induced neuropraxia by decreasing the activation threshold of tissue nociceptors and the conduction velocity of nerve signals conveying pain. Published studies evaluating ice as topical anesthesia in dentistry have been reported, in addition to the intra-oral use of “refrigerant solutions” and “Vapocoolants” (such as 1,1,1,3,3-pentafluoropropane/1,1,1,2-tetrafluoroethane) in palatal injections in adults. Although the effect of the refrigerant agent was found to be superior to BC20%, the use of ice and refrigerants as topical anesthetics of the oral mucosa is not widely used in dentistry, and appears to be non-existent in children.

Ethyl Chloride (EC) is a topical anesthetic agent used prior to rapid invasive techniques in minor surgery and sports medicine. Historically, EC had been used as a general anesthesia agent for dental extractions. However this practice ceased, with a focus on using it as a topical skin anesthesia agent and its uses as a sensibility testing agent for teeth. When applied by aerosol on the skin, its rapid vaporization causes a tissue cooling of up to -20°C, generating an insensitivity of the peripheral nerves and, consequently, immediate local anesthesia lasting for

a few minutes. It does not present incompatibilities, interactions, or side effects beyond a local and transient hypersensitivity due to the cold. It had been suggested that because EC has a rapid effect, it can safely provide *cutaneous* analgesia in children in circumstances when it is impractical to wait for other local anesthetic preparations to take effect. This could be extrapolated to the oral cavity and dentistry. However, as far as the authors know, although there is a registered trial ongoing at the moment  comparing EC effect on the oral mucosa in comparison to Lidocaine 5%, none have compared EC to BC 20% intraorally in children. Therefore this study aims to describe a new method of topical anesthesia of oral mucosa pre-local anesthesia injection and to compare the perceived pain, and subjective experience of two topical anesthetic agents, BC 20% gel and indirect application (using cotton palettes) of Ethyl Chloride spray.

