# Appendix I

AutoSave OFF research Excel sheet — Saved to my Mac

Home Insert Draw Page Layout Formulas Data Review View Tell me

Calibri (Body) 12

B I U

Merge & Center

General

Conditional Formatting Format as Table Cell Styles

Insert Delete Format

	A	B	C	D	E	F	G	H	I	J	K	L	M	N	O	P	Q	R
1	SN	Gender	AGE	LA Infiltration	Group	INDICES												
2						H.R	VAS	FP	SEM									
3	1																	
4	2																	
5	3																	
6	4																	
7	5																	
8	6																	
9	7																	
10	8																	
11	9																	
12	10																	
13	11																	
14	12																	
15	13																	
16	14																	
17	15																	
18	16																	
19	17																	
20	18																	
21	19																	
22	20																	
23	21																	
24	22																	
25	23																	
26	24																	
27	25																	
28	26																	
29	27																	
30	28																	

Gender	Group		Indices			
M 1/ F 2	A BCG	B EC	(H.R) Heart Rate / bpm	(VAS) Visual analog scale	(F.P) facial pain scale	(SEM) Sound Eye Motor

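### No harm, refusal or tolerability item for the topical application appears in either arm, so the subjective-experience comparison is only partly supported and no harms data would result

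*Combined protocol and SAP*

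**What the plan says.** The Introduction gives the case for EC and the only safety statement about it. It describes the agent's action on skin: "When applied by aerosol on the skin, its rapid vaporization causes a tissue cooling of up to -20°C". It then says: "It does not present incompatibilities, interactions, or side effects beyond a local and transient hypersensitivity due to the cold". A further sentence on paediatric use concerns analgesia of the skin, and the authors add: "This could be extrapolated to the oral cavity and dentistry". They describe ice and refrigerants on oral mucosa as little used in dentistry, "and appears to be non-existent in children".

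The same section explains why an alternative to gel is wanted. Gels spread, may taste unpleasant or cause discomfort, and "there is a risk of allergic reactions to several components in the different gels available for topical anesthesia". It closes by stating an intention to "compare the perceived pain, and subjective experience of two topical anesthetic agents".

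The formal Aims and Specific objectives are narrower. They name efficacy against injection pain, physiological change, reported and observed pain by age and gender, and the description of a new technique. Safety is not among them.

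Section D and the legend to Fig 1 give four outcomes: heart rate, SEM, VAS and a face scale. Section F names one data-capture instrument, the Appendix I sheet. Its columns are serial number, gender, age, infiltration, group, heart rate, VAS, FP and SEM.

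**The concern.** The plan brings a skin agent to the oral mucosa of children aged 7 to 10 by a route it calls new. It justifies this partly by the drawbacks of gel, then measures neither those drawbacks nor their EC counterparts. A child could find the cold application unpleasant, refuse it, or show a change at the site, and still report a mild injection. The sheet would then show only a good result.

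Three things are at stake. A mucosal reaction could go unrecorded. The trial could not say whether EC improves on gel in taste, discomfort or allergy. A difference between arms in how many children completed the application would also be invisible, although it bears on how the pain comparison is read. None of this can be recovered after data collection.

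**Working it through.** **Step 1. What each measure covers (Section D, Appendix I).**

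| Measure | When or what | Covers the topical application? |
|---|---|---|
| Heart rate | Just before and just after the injection | No |
| SEM | Assessor's observation of pain while the anesthetic is infiltrated | No |
| VAS | Child's rating after the injection | Not asked separately |
| Face scale | Child's rating after the injection | Not asked separately |
| Adverse event, mucosal change, refusal, taste or cold discomfort | No procedure or column found | No |

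Section H plans no analysis of harms. Allergy appears only as an exclusion criterion in Section B.

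**Step 2. Set this against the Introduction.** It lists subjective experience alongside perceived pain as something to compare. Injection pain is measured by child self-report, so that part is covered. Experience of the application itself is not.

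**Step 3. What recording could show at the planned size.** The documents give no reaction rate and no harms calculation, so there is no planned figure on harms to reproduce. The one input is 21 children per arm, from Section C. (The printed sample-size formula does not give 21. With a standardised difference of 1.67, two-sided 5% and 80% power, it gives 15.70 / 1.67² = 5.63, so 6 per arm. The tabulated 21 is 12.4 × 1.67 = 20.7. That is a separate matter; 21 is used here as the planned enrolment.)

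Exact upper limit when 0 of n children have an event:

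- One-sided 95%: 1 − 0.05^(1/21) = 0.133
- Two-sided 95%: 1 − 0.025^(1/21) = 0.161

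Chance of at least one event among 21 children, 1 − (1 − p)^21, over a range of assumed true rates p:

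| Assumed rate | Chance of at least one event |
|---|---|
| 1% | 19% |
| 2% | 35% |
| 5% | 66% |
| 10% | 89% |

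For a comparison between arms, assumed rates of 5% and 20% would give power of about 31% (normal approximation, rough at this size). Counts with intervals are therefore the realistic output, rather than a test.

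**Step 4. Without the fields.** There is no count, so no bound on any rate in either arm.

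**The case against.** The strongest reply is that the trial is not a safety study. The aim, objectives, research question and null hypothesis all concern pain and physiology, and the safety sentence is cited background. That is correct. A reader might infer that a stated safety objective fails, but the documents state none. What is missing is a harms outcome.

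Four other inferences go too far:

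- **That the subjective-experience aim has no support at all.** VAS and the face scale are child self-reports, and the phrase is not carried into the formal objectives. What is unmeasured is experience beyond injection pain.
- **That the mucosa is cooled to -20°C.** That figure is for aerosol sprayed directly on skin. Here a cotton palette is sprayed from 10 cm and then applied for 30 seconds. The documents do not give the temperature under it.
- **That Appendix I proves harms are recorded nowhere.** The sheet has one heart-rate column although Section D requires two readings, so it does not list everything planned. Removed pages, the consent form and the flow-chart figure could contain harms wording.
- **That EC in the mouth is wholly new.** The Introduction mentions its use in testing teeth, intra-oral refrigerants in adults, and an ongoing registered trial of EC on oral mucosa. What is presented as new is this topical method in children.

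There is also a practical objection. The blinded assessor collects the data, and mucosal appearance or comments on cold and taste could reveal the arm. A rating of the application taken before the injection could also influence the pain scores. Both points stand, and they determine who should record and when. They do not remove the gap.

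**Conclusion.** The point holds in a limited form. In the available text, no adverse-event, mucosal-reaction, refusal or application-tolerability item is recorded in either arm, and every outcome is tied to the injection. The comparison of subjective experience is supported for injection pain only. The trial would give no data on the harms of an agent whose safety statement rests on skin use.

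The gain from recording is modest. With 21 EC children, zero events would exclude only rates above about 16% (two-sided 95%) or 13% (one-sided). Reactions with a true rate near 10% would probably be seen; those near 1% or 2% probably would not. These figures assume that all 21 children are observed and that events are independent between children; the true rates are illustrative. The pain comparison's error rates and power do not change. This is worth correcting before recruitment, but it does not undermine the primary comparison.

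**What to change.** Add four fields to Appendix I, identical in both arms:

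1. Any adverse event during the visit.
2. Visible mucosal change at the site after the topical application and before needle entry, with a short description. Inspecting then avoids confusion with the puncture and the adrenaline-containing injection.
3. Refusal or early removal of the topical agent.
4. A brief child rating of the application (cold, taste, discomfort).

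The operator, who opens the envelope and so knows the arm, should complete these on a part of the sheet that the blinded assessor does not see. The child's rating should come after SEM, VAS and the face scale are complete, so that it cannot influence them.

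In Section H, add a line: counts by arm with exact 95% confidence intervals, no claim of safety beyond those intervals, and a statement that 0 of 21 would exclude only rates above about 16% (two-sided).

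The cost is about a minute per child from staff already present, plus the work of keeping these fields from the assessor. Two limits remain. The child's rating of the application is given after the injection and may be coloured by it. A reaction that appears after the visit would still be missed.

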### 3. Aims of the study

---

To compare the efficacy of 20% Benzocaine (BC) gel and indirect application of Ethyl Chloride (EC) spray, in reducing pain perception during local anesthesia infiltration in pediatric patients as well as describe a new simple method for topical anesthesia.

#### Specific objectives

- To compare the efficacy of BC and EC on buccal infiltration.
- To compare the physiological changes observed during the administration of local anesthesia with two pre-anesthesia topical application techniques (BC and EC).
- To compare the reported and observed pain perception of two topical anesthetic techniques (BC & EC) with different age groups and gender.

### Research question

- How effective is the indirect application of EC topical spray anesthesia on pain perception during intraoral buccal injection in children in comparison to BC 20%?

### Null Hypothesis:

- There is no difference between EC topical anesthesia and BC 20% topical gel on the pain perception buccal during infiltration.

## 4. Materials and Methods

---

### **Study Design**

The proposed study is a randomized control trial, single-blinded, following CONSORT Group, and Standard Protocol Items: Recommendations for Interventional Trials reporting guidelines.

### **Population:**

All healthy children and adolescents aged 7 to 10 seeking pediatric dental care who meet the inclusion criteria and sign the consent form (Appendix II).

## PARTICIPANTS, INTERVENTIONS, AND OUTCOMES

### A. Study Design / Location/ Candidates

The proposed study is a single-blinded randomized control trial. The study will investigate the pain perception during buccal infiltration using indirect EC spray ( spraying EC 10 cm distance of the cotton palette and applied on the oral mucosa for 30 seconds at the site of injection prior

to local anesthesia injection) topical anesthesia and BC 20% topical gel applied for 30 seconds on dried oral mucosa and left for 1 minute using the end of an applicator stick (among seven to 10-year-old school children who attended Pediatric Dentistry Department at Dubai Dental Hospital (DDH), Mohammed Bin Rashid University (MBRU) in Dubai, the United Arab Emirates (UAE).

## **B. Eligibility criteria**

### **Inclusion criteria**

- Healthy children (ASA I) aged between 7 – 10 years old.
- Needing any maxillary buccal infiltration (anterior, middle, posterior)
- Had no prior history of local anesthesia.
- Frankl behavior III or IV
- Not taking any painkillers, or other drugs that would influence with their pain perception.

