### **Exclusion Criteria**

- History of a medically compromised condition and intellectual disability.
- Any allergy to local anesthesia.
- Active pathology at the site of injection.
- Prior history of intra-oral injection.
- Frankl behavior I or II.
- Children/parents not willing to participate in the study.
- Needle phobia.
- Patients require treatment under conscious sedation.

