## **D. Procedure and Indices:**

### **Randomization, Blinding and the procedure with topical anesthesia (EC or BC):**

Pre-local analgesia topical BC or EC technique will be selected randomly and applied per the protocol. A single calibrated operator (A.A) using randomly selected sealed envelopes that have been previously divided equally according to sample size arms. The selected envelope is then opened by the operator, who applies either the EC or BC topical anesthesia technique based on the chosen envelop. Followed by maxillary local analgesia buccal infiltration for a single tooth by a calibrated operator (A.A). The child is then observed and assessed by the blinded primary investigator (N.A) (to the topical anesthesia technique) for pain perception during local anesthesia infiltration based on the Sound, Eye, Motor index used in this study. The child is then asked to rate the Visual Analog Scale and Facial Pain Scale. Heart rate of the patient will be recorded as per below protocol.

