#### **1- Heart rate (HR)**

Physiological changes in HR will be measured in beats per minute (bpm) and registered using a pulse oximeter. Each participant's heart rate will be recorded immediately before and after the injection using an FDA-approved pulse oximeter (SantaMedical SM-165 Fingertip Pulse Oximeter ®, China). The injection site will be dried and isolated using a cotton roll. A small

[figure not shown]
quantity of the topical anesthesia 20% Benzocaine (Dharma Research, Miami, USA®) anesthetic gel will be applied using the end of an applicator stick directly at the site of penetration for 30 s and then left for 1 min to ensure effectiveness. All the time periods will be calculated using the clock App timer available on an iPhone®. The injection of the anesthetic solution is performed according to the standard technique mentioned below. Directly after the injection, the pulse rate will be recorded a second time.

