## I. Ethical considerations

---

All patients fulfilling the basic inclusion criteria will be eligible for participation. The Principal Investigator will be responsible for identifying those prospective patients who do not fulfill the eligibility criteria so that they are not approached. Eligible patients will be approached in the clinic, invited to participate and subsequently examined by the clinical investigator to verify eligibility. The purpose of the study will be explained to parents/guardians and the consent

form will be provided to those who fulfill the study and assent/agree to participate. Children and parents/guardians will be given time to carefully read the consent form. It will ensure that they fully understand the consent form, and any questions will be answered. The participants will be expected to assent, i.e., affirmatively agree, to participate in the research project, and their parents/guardians will provide consent. The researcher obtaining informed consent will not be providing the treatment in order to avoid any appearance of undue coercion.

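### Frankl level (III or IV) is judged before treatment but has no field on the data sheet and no place in the SEM analysis, so chance imbalance in behaviour cannot be shown or adjusted for

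*Combined protocol and SAP*

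**What the plan says.** - **Eligibility (section B).** Children must show "Frankl behavior III or IV"; those at "Frankl behavior I or II" are excluded. Two levels are therefore admitted.
- **Timing of the judgement (section I, Ethical considerations).** Children who are invited are "subsequently examined by the clinical investigator to verify eligibility".
- **Allocation (section D).** The operator uses "randomly selected sealed envelopes that have been previously divided equally according to sample size arms". No stratification factor is named.
- **SEM (section D).** The blinded investigator assesses the child "for pain perception during local anesthesia infiltration based on the Sound, Eye, Motor index used in this study". No earlier SEM score is planned. The text under the SEM heading describes a faces scale, so the documents do not set out how SEM is scored.
- **Other pre-injection measurement (section D, item 1).** Only heart rate has one: "heart rate will be recorded immediately before and after the injection".
- **Data sheet (section F and Appendix I).** The proforma has columns for serial number, gender, age, infiltration, group, heart rate, VAS, faces scale and SEM. Neither the columns nor the legend mention Frankl.
- **Analysis (section H).** Two-arm tests, parametric or non-parametric depending on a normality test. No covariate is named.

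**The concern.** The protocol treats behaviour before treatment as important enough to exclude the two lower Frankl levels, and SEM then scores behaviour during the injection. It is plausible that a child at level III reacts more visibly than a child at level IV, whichever topical agent is used. With about 21 children per arm and no stratification, the arms can differ by chance in their share of level III children.

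On the planned data, nobody could see whether that happened, because there is no value to tabulate. Nor could the analyst remove the part of the SEM variance that goes with Frankl level. At stake are some precision on SEM and the reader's ability to check that the arms started with similar behaviour. The value would be hard to recover reliably after treatment.

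**Working it through.** **Planned size.** Section C states 21 per arm. Its table reaches this as 12.4 × 1.67 = 20.7. The printed formula with its own inputs (difference 20.67, SD 12.41, two-sided 5%, 80% power) gives 15.70 / 1.67² = 5.6, that is 6 per arm. That discrepancy is a separate matter. Here n = 21 per arm is used only as the number the trial plans to enrol.

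**Assumptions (not in the documents).**
- Share of enrolled children at Frankl III: p = 10% to 50%.
- Gap in mean SEM between levels III and IV: d = 0.5 to 1.2 within-level SD.
- Alternatively, a direct correlation of Frankl level with SEM of 0.1 to 0.3, so R² = 1% to 9%.

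**Step 1: chance imbalance.** Take the level III counts in the two arms as independent Binomial(21, p). Four children are 4/21 = 19 percentage points.

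| p | P(arms differ by ≥ 4 children) |
|---|---|
| 10% | 0.070 |
| 20% | 0.174 |
| 30% | 0.237 |
| 50% | 0.280 |

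**Step 2: what such an imbalance does, and how much Frankl could explain.** In units of the total SEM SD, a four-child imbalance shifts the arm difference by d × (4/21) / √(1 + p(1−p)d²). The share of variance explained is R² = p(1−p)d² / (1 + p(1−p)d²).

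| p | d | R² | Shift (SD) |
|---|---|---|---|
| 30% | 0.5 | 5.0% | 0.09 |
| 30% | 1.2 | 23.2% | 0.20 |
| 50% | 0.5 | 5.9% | 0.09 |
| 50% | 1.2 | 26.5% | 0.20 |

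The unadjusted standard error of the arm difference is √(2/21) = 0.309 SD, so these shifts are about 0.3 to 0.65 of one standard error. The largest R² that these inputs allow is 26.5%.

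**Step 3: gain from adjustment.** With 21 per arm and two-sided 5%, the unadjusted t-test (40 df) has 80% power for an effect of 0.886 SD (non-central t). Adjusted power uses 0.886/√(1−R²) with 39 df. The interval width scales by √(1−R²). The equivalent unadjusted size is 21/(1−R²) per arm.

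| R² | Power | Interval width | Equivalent n per arm |
|---|---|---|---|
| 0% | 79.9% | 1.000 | 21.0 |
| 1% | 80.3% | 0.995 | 21.2 |
| 5% | 81.9% | 0.975 | 22.1 |
| 9% | 83.5% | 0.954 | 23.1 |
| 26.5% | 90.4% | 0.857 | 28.6 |

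The first row shows the price if Frankl level is unrelated to SEM: the critical t value rises from 2.021 (40 df) to 2.023 (39 df), which is negligible.

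**The case against.** **A reader might infer that the SEM comparison is biased, or that SEM is invalid for want of a baseline.** The documents do not support this. A comparison of post-treatment scores only is valid in a randomised trial. A chance imbalance of the size above is ordinary random variation, already covered by the test and the interval, so the shift in step 2 must not be added to the precision loss as a second harm. Frankl is also a different scale: it would be a covariate, not an SEM baseline.

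**A reader might infer that the trial discards a recorded rating.** The eligibility rule strictly needs only a check that the child is at level III or better. Appendix I also looks schematic: it shows 28 numbered rows against 42 planned children, and one heart-rate column against two planned readings. Other eligibility items, such as ASA class, are not on it either. A clinic note might hold the rating. This stands as a limit on the wording. It does not remove the point, because the documents plan no other trial record of Frankl level.

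**A reader might infer that SEM is the only blinded outcome.** This is too strong. The investigator who is described as blinded also collects the data, and the documents do not address the child's own awareness of the agent.

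**The gain may be small.** Needle phobia, previous intra-oral injection, sedation cases and the lower Frankl levels are all excluded, so only two adjacent levels remain. The trial is sized on VAS, where the planned effect of 1.67 SD has unadjusted power above 99.9% at 21 per arm; the 80% benchmark for SEM is chosen here for illustration. All of this stands, and it is why the range starts near zero.

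**Conclusion.** The point holds as a low-cost improvement, not as an error. Frankl level is judged before treatment, but it appears on no planned data sheet and in no planned analysis. The planned data can therefore neither display a chance imbalance in pre-treatment behaviour nor use that behaviour to improve precision on SEM.

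The size depends on quantities that the documents do not give. A difference of four or more children between arms has probability of about 7% to 28% for 10% to 50% Frankl III. For an effect with 80% unadjusted power, adjustment gives about 80% to 84% at R² of 1% to 9%. It gives at most about 90%, with an interval about 14% narrower, at the assumed ceiling of 26.5%. The power figures treat SEM as roughly continuous with a linear model, which the undocumented scoring does not guarantee.

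**What to change.** 1. Add a column to Appendix I, 'Frankl (III=3 / IV=4)', completed at the eligibility examination before the envelope is opened.
2. Report the Frankl split by arm in the baseline table.
3. In section H, pre-specify that SEM is compared between arms with Frankl level as a covariate in a linear model or, if ranks are used, as a stratum in a van Elteren test.

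Keep the allocation method as it is. Separate envelope sets per Frankl level in small blocks would make the next allocation easier to guess for the operator, who opens the envelopes and applies the treatment, and could leave unequal arms. Adjustment in the analysis captures the precision without that risk.

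The cost is one column and one degree of freedom, with no extra visit, procedure, assessor or patient. If Frankl level proves unrelated to SEM, the loss of precision is negligible.
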